10.1. Sample size

As a pilot laboratory research study with aim of revealing novel associations, a formal power calculation is not possible, since no previous data is available. The sample size is based on previous experience with similar projects and feasibility. The data from this study will be used to calculate sample sizes for future larger scale studies.

10.2. Method of analysis

For the major body of translational laboratory experiments appropriate parametric and non-parametric tests will be conducted using GraphPad Prism. For experiments assessing associations of detected auto-antibodies to clinical variables, linear regression analyses will be undertaken in R, and ROC AUC analysis of capacity of serum auto-antibodies to detect severe eosinophilic diseases undertaken.

11. Ethics

The Chief Investigator will ensure that the study is carried out in accordance with the ethical principles of the UK policy framework for health and social care research (2017) and its subsequent amendments as applicable, as well as applicable legal and regulatory requirements.

The research team has no financial or other competing interests for this study.

Human genome (gDNA) analysis will not be conducted as part of this research project.

Clinically defined immunodeficiencies will not be tested for as part of the immunological analyses.

The CRF and samples for immunological analysis will be anonymised so donors are not known to the research team or anyone reviewing the analyses and results.

Invitation to participate and consent will be undertaken on the same day. Potential participants will be given as long as they require to review the PIS and ask questions before deciding whether to participate. The study clinical procedure (taking of a blood sample of 50ml maximum volume) carries minimal risk. Donor decisions to participate or not in the study will not affect their health or clinical care. We therefore feel this is an appropriate period for informed consent for this low-risk study. Requiring potential volunteers to come back on a second occasion to give informed consent and samples would not facilitate ethical recruitment of patients, many of whom need to travel significant distances to Barts Health/Royal Free Hospitals for appointments and many of whom have significant chronic ill health.

11.1. Annual Safety Reporting

The CI will send an Annual Progress Report to the REC and the sponsor using the HRA template on the anniversary of the REC “favourable opinion”.

12. Public involvement

There has been no specific public involvement in the development of this protocol for exploratory translational laboratory research. However this research is commensurate with the research strategies suggested by patient advocacy groups such as Asthma UK and the European Asthma Research and Innovation Partnership (EARIP) asthma research roadmap which themselves had extensive public and patient involvement.

13. Data handling and record keeping

13.1. Data management

The personal data of each patient will be stored in hard copies using paper-based consent forms, paper CRFs and associated data in a secure locked filing cabinet in a locked room. Only members of the research team, monitors and/or regulatory bodies will have access to the physical hard copy of this data and are authorised to do so.

13.2. Source data

Case Report Form (Patients) data variable list:

1. Age
2. Gender
3. Ethnicity (optional)
4. Occupational history
5. Confirmation participant meets Inclusion and Exclusion criteria (Yes/No)
6. Smoking history
7. Diagnosed medical condition(s) and basis for diagnoses with focus on diagnostic criteria for Severe Eosinophilic Asthma, EGPA
8. Suspected medical conditions(s)
9. Immunosuppressive medication(s) dose regimes and history
10. Previous treatment history, especially corticosteroid history
11. Full blood count (haematology)
12. Most recent and previous FeNO breath tests, if done
13. Auto-immune serology results
14. Spirometry and gas transfer tests, if done
15. Highest previous blood eosinophil count, ANCA serology (immunofluorescence, anti-PR3 and anti-MPO antibody titre) and trend
16. Investigations for target organ involvement in patients with suspected vasculitis including histology
17. Clinical disease activity measures (for example Birmingham Vasculitis Activity Score (BVAS), Asthma Control Questionnaire (ACQ)-6)

Case Report Form (Healthy Control) data variable list:

1. Age
2. Gender
3. Ethnicity (optional)
4. Occupational history
5. Confirmation participant meets Inclusion and Exclusion criteria (Yes/No)
6. Smoking history

13.3. Confidentiality

Information related to participants will be kept confidential and managed in accordance with the Data Protection Act, the General Data Protection Regulation (GDPR), NHS Caldecott Principles, UK policy framework for health and social care research (2017), and the conditions of Research Ethics Committee Approval.

Each patient will be assigned a unique study number. Patients' initials and date of birth in the format dd/mm/yy will be used as a means of confirming patient identity for audit checks. This information will be kept in an encrypted screening log, which will be updated throughout the study and stored on a secure server. Only patient study IDs will be used on paper CRFs and samples (pseudoanonymisation). The subject will be identified by a study specific subject number. The patient's name will NOT be included in any CRF or sample.

13.4. Record Retention and Archiving

When the research trial is complete, records will be kept for a further 5 years.

14. Laboratories

Samples will be analysed at the EMR laboratory, Queen Mary University of London: EMR Laboratory (QMUL)

[name] (Laboratory Manager)

Centre for Experimental Medicine and Rheumatology

[name], William Harvey Research Institute Barts and the London School of Medicine and Dentistry

Queen Mary University of London, [name]

[name]

Samples will be processed on day of receipt of the samples (within 24 hours of sampling). Following processing, all samples will be stored immediately in -80C freezers or subject to analysis as described below within 48 hours.

- Samples will be analysed in the QMUL laboratories at William Harvey Research Institute as follows to investigate the major Study Outcomes:

INDIRECT IMMUNOFLUORESCENCE ASSAYS

Eosinophils will be cultured in preparatory experiments from the EoL-1 eosinophil cell line and in definitive experiments isolated from patients with eosinophilia in the context of severe asthma. Slides of cell smears will then be prepared of inactive eosinophils and those activated to undergo piecemeal degranulation and cytolysis with eosinophil extracellular trap formation. Cell smears will be examined unmodified and after post-translational modification of proteins. Fixed slides will then be incubated with dilutions of serum and sol phase sputum supernatant from patients and healthy controls, and incubated with fluorescein-conjugated anti-human immunoglobulin antibody before being examined by fluorescent microscopy and fluorescence intensity measured. Confocal microscopy and complementary fluorescein-conjugated antibody markers will be used to examine characteristics of target antigens for patient serum auto-antibodies.

TARGET PROTEIN ASSAYS

Eosinophil proteins such as those previously identified as of importance (e.g. eosinophil-peroxidase, *EPX*) and also novel candidate proteins specific to eosinophils (including *ARFIP1*, *BCL2A1*, *PPCDC*, *SLC12A6* etc) as identified by FANTOM5 geneset analysis will be purchased or synthesised in Expi-293 cells, by obtaining tagged clones from Origene and developing stable expressing cell lines. Protein synthesis be confirmed by western blot. Proteins will be used to coat ELISA plates with/without prior post-translational modification. Presence of donor serum antibodies in serum and in sputum will then be examined by ELISA using appropriate enzyme-

linked secondary antibodies. Similar extracellular matrix proteins such as collagen V will be investigated.

POST-TRANSLATIONAL MODIFICATION OF PEPTIDES

Eosinophil suspensions / slides and commercially sourced / synthesised target proteins (e.g. eosinophil peroxidase and collagen V) will be modified as follows:

Oxidative modification – by hydroxyl radical exposure with hypochlorous acid using our established methodology (Strollo, Vinci et al. 2015). Citrullination – by recombinant peptidylarginine deiminase (PAD).

Ambient pollutants and nanopollutants are known to be able to induce both oxidative stress and protein citrullination as well as potentially direct eosinophil activation. Given the known association between asthma and ambient pollution we will additionally examine potential serum antibodies to ambient pollution particulate matter stimulated/modified eosinophil and collagen proteins.

- Samples may also be analysed to address associated Exploratory Outcomes, to examine immunological mechanisms underpinning auto-antibody disease associations. Applicable experimental techniques to include:

Blood and sputum leukocyte phenotyping *ex vivo* by flow-cytometry (FACS) analysis of circulating immune cell subsets (including myeloid-lineage cells, conventional/unconventional lymphocyte populations, and granulocyte populations).

In vitro culture of blood and sputum leukocytes (whole sample cultures, fractionated peripheral blood mononuclear cells, and magnetically separated / FACS-sorted leukocyte subsets) to assess responses to a variety of subset-specific agonists and stimuli. Positive and negative controls to be included as appropriate. Key mediators of these responses may be identified using small molecule inhibitors, blocking antibodies, recombinant cytokines/proteins, essential supplements/chelators, and other equivalent culture additives according to cell type and function of interest. Responses to be assessed using multicolour flow-cytometry methods, advanced imaging techniques (INCell analysis, immunofluorescence and confocal microscopy, ImageStream), quantification of cytokine/chemokine/antibody release by ELISA / multiplex bead array, and measurement of gene expression by PCR / RNA-seq methodology (mRNA but not gDNA). To include B-ELISpot (B lymphocyte enzyme-linked immune absorbent spot) assays to further examine auto-antigen specific immune responses.

Isolated proteins may be examined by immunoblotting, proteomics, mass spectrometry, surface plasmon resonance / microscale thermophoresis, and other equivalent binding studies.

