5.1. Background

The pivotal importance of eosinophils in the pathology of severe asthma and eosinophilic granulomatous polyangiitis (EGPA) is increasingly evident given the success of anti-eosinophil biologic therapies. The source of eosinophil stimulating IL-5 in severe asthma is now thought to be ILC2 cells. However the persistent chronicity of the airways inflammation in the absence of an exogenous stimulus in most patients is unexplained and of major research importance. This suggests the presence of an endogenous stimulus of persistent auto-reactive airways inflammation - an auto-immune hypothesis for severe asthma pathology - which with molecular spread could then potentially lead to the systemic disease of EGPA (Mukherjee and Nair 2018).

Auto-antibody responses have been reported in patients with asthma (Mukherjee and Nair 2018). For example Lott and colleagues have detected auto-antibodies to type V collagen in asthmatic individuals (Lott, Sehra et al. 2013). Similarly Liu and colleagues have reported auto-antibodies to type V collagen in asthmatic patients, as well auto-antibodies to other proteins such as Activin A receptor, with clinical correlates to markers of asthma severity (Liu, Subramanian et al. 2012). However auto-antibodies within the pulmonary compartment, as detected in sputum, may be more important than auto-antibodies in serum (Qin, Long et al. 2019). In particular auto-antibodies to eosinophil peroxidase in sputum is a feature of severe eosinophilic asthma (Mukherjee, Bulir et al. 2018).

Anti-neutrophil cytoplasmic antibodies (ANCA), especially anti-myeloperoxidase antibodies, are present in a proportion of patients with EGPA but absent in a similar proportion. Similar perinuclear ANCA is also present in inflammatory bowel disease. These issues raise the question of whether ANCA in EGPA is an epiphomenon or pathological.

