7.1. Inclusion criteria

- *Informed consent*
- *Age 18 years and over*
- *Patients:*
 - *Severe Eosinophilic Asthma*
(*with multi-disciplinary diagnosis as per ERS/ATS Criteria, blood eosinophils $\geq 0.3 \times 10^9/L$ on inhaled corticosteroids*); or
 - EGPA*
(*as per American College of Rheumatology (ACR) Criteria*); or
 - Eosinophilic COPD*
(*post-bronchodilator FEV1/FVC $< 70\%$ predicted, absence of bronchodilator reversibility, > 20 pack year smoking history, no medical history of current asthma, blood eosinophils $\geq 0.3 \times 10^9/L$*); or
 - Eosinophilic oesophagitis*
(*with diagnostic histology*); or
 - Granulomatosis with Polyangiitis (GPA, formerly called Wegener's)*
(*as per American College of Rheumatology (ACR) Criteria*)
- *Healthy Controls:*
 - *No acute medical illness.*
 - *No diagnosed chronic respiratory disease, allergy or infective condition, including no history of asthma.*
 - *No history of EGPA or other vasculitis,*
 - *No systemic immunosuppressive medication.*

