7.2. Exclusion criteria

- *Any inclusion criteria not met*
- *Known Pregnancy*
- *Anaemia*
- *Donation of more than 240mls blood in the last sixteen weeks (four months) to any other research study or as a donation to the National Blood Transfusion Service*
- *Rituximab, plasmapharesis or polyclonal immunoglobulin infusion (ever)*

8. Study design

Study Visit (Patients)

This is a single study visit encompassing patient recruitment, consent, data collection and provision of a peripheral blood sample with/without concurrent sputum sample, with no follow-up visits.

Patients will be recruited via Outpatient Clinics conducted at St Bartholomew's (Bart's) Hospital, The Royal London Hospital, and Mile End Hospital (all Bart's Health NHS Trust), Royal Free London NHS Trust, as well as from inpatients at these hospitals under the care of the Respiratory Medicine and Rheumatology teams (including those under other services needing inpatient respiratory medicine or rheumatology review).

Potential patients will be identified by their clinical team and invited to participate. If interested they will be given a Participant Information Sheet (PIS). Informed Consent and Screening will be undertaken by a GCP-trained member of the clinical team or GCP-trained researcher. An anonymised data collection case report form (CRF) will be completed by a member of the clinical team and a linked (anonymised) blood sample collected by a staff member trained in phlebotomy. If the patient is able to spontaneously produce sputum, and there is no clinical concern about TB infection, then they will be asked to cough a sample in to a sterile sample pot.

The linked anonymised CRF and samples will then be taken to the research laboratories at QMUL for immune cell analysis. Laboratory immunology studies will be conducted by as per protocol (Section 14) by a dedicated Post-Doctoral Research Assistant.

Study Visit (Healthy Controls)

There is a single study visit encompassing healthy control recruitment, consent, data collection and taking of blood sample, with no follow-up visits.

Healthy controls will be recruited at QMUL, Bart's Health and Royal Free sites via poster advertisement.

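### Therapeutic antibodies directed at eosinophils are not excluded, not specifically recorded and not handled in the analysis, so in the immunofluorescence arm a drug could read as an auto-antibody in cases only

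*Combined protocol and SAP*

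**What the plan says.** **Assay.** The immunofluorescence part of section 14 uses whole eosinophils, "in definitive experiments isolated from patients with eosinophilia in the context of severe asthma". "Fixed slides will then be incubated with dilutions of serum and sol phase sputum supernatant from patients and healthy controls", and the slides are then "incubated with fluorescein-conjugated anti-human immunoglobulin antibody before being examined by fluorescent microscopy and fluorescence intensity measured". No isotype restriction, blocking step or drug-interference control is described.

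**Eligibility.** Section 7.2 lists "Rituximab, plasmapharesis or polyclonal immunoglobulin infusion (ever" among the exclusions, and no other antibody treatment. Section 5.1 nevertheless opens by arguing for the importance of eosinophils in severe asthma and EGPA "given the success of anti-eosinophil biologic therapies". Under section 7.1, healthy controls may have no asthma, chronic respiratory disease, allergy or vasculitis, and "No systemic immunosuppressive medication".

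**Data capture.** In section 13.2, patient CRF item 9 is "Immunosuppressive medication(s) dose regimes and history" and item 10 is "Previous treatment history, especially corticosteroid history". Neither names biologics or asks when the last dose was given.

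**Analysis.** The covariates in section 6 are disease duration, atopy, nasal polyps, gender and age. Treatment with a therapeutic antibody is not among them, nor among the patient subsets listed there. Section 10.2 names parametric and non-parametric tests, linear regression and ROC AUC, and says nothing about drug-exposed samples.

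**The concern.** The agnostic arm is meant to find unknown antibodies by looking for human immunoglobulin on eosinophils. A therapeutic human or humanised antibody that binds the eosinophil surface would give the same signal. At least 60 patients come largely from specialist severe asthma and rheumatology services, where such treatment is plausible, while the control criteria make exposure very unlikely. Any interference would therefore fall on one side of the comparison: staining in severe eosinophilic asthma and EGPA, none in controls. That is also the pattern the study hopes to report.

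The protocol already recognises that treatment can distort antibody measurements, since it excludes rituximab, plasmapheresis and polyclonal immunoglobulin. It leaves out antibodies aimed at the assay's own target cell. A false lead could travel: section 6 takes candidates into a wider patient group, and section 10.1 intends the data to size later studies. Section 8 allows one visit and no follow-up, so a last-dose date not collected then may be hard to recover.

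**Working it through.** The plan has no figure of its own to reproduce, because section 10.1 gives no power calculation. What follows is an illustration of size.

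**Inputs from the protocol**
- Cases with severe eosinophilic asthma and/or EGPA: at least 60 (section 7).
- Healthy controls: 30 (sections 4 and 7).

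**Assumptions, none of them in the protocol**
- A fraction p of the 60 cases carries an antibody that binds an eosinophil surface target. Range 10-25%, with 0 as reference.
- No control carries one.
- No real auto-antibody exists.
- Worst case: every exposed serum reads positive and above all controls.
- Background positivity b in all other samples: 0%, 5% or 10%.

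**Step 1: spurious positives.** 60 × 0.10 = 6; 60 × 0.25 = 15.

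**Step 2: AUC if the reading were used in a ROC analysis.** Exposed cases always outrank controls and the rest do so half the time:

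AUC = p × 1 + (1 − p) × 0.5 = 0.5 + p/2

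- p = 0: 0.50
- p = 0.10: 0.55
- p = 0.25: 0.625

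**Step 3: chance of a nominally significant difference.** Case positivity is b + (1 − b)p; for example, b = 0.05 and p = 0.10 give 0.05 + 0.95 × 0.10 = 0.145. Enumerating all outcomes for 60 against 30 with Fisher's exact test at two-sided 0.05 (the protocol sets no significance level) gives:

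| Background b | p = 0 | p = 10% | p = 20% | p = 25% |
|---|---|---|---|---|
| 0% | 0% | 25% | 93% | 99% |
| 5% | 2% | 18% | 60% | 80% |
| 10% | 3% | 13% | 48% | 66% |

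**Step 4: the AUC shift against chance.** The standard error of a null AUC is √[(60 + 30 + 1)/(12 × 60 × 30)] = √(91/21,600) = 0.065. A shift of 0.05 is 0.8 standard errors and a shift of 0.125 is 1.9. The distortion is therefore modest on the AUC scale at low exposure, and larger for a positive/negative comparison when background positivity is low.

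**Step 5: where it applies.** The ELISAs in section 14 coat plates with selected purified proteins. A drug would register there only if the coated protein were its target. The exposure problem is thus confined largely to the immunofluorescence arm.

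**The case against.** The strongest reply has five parts.

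- **Treatment is recorded.** A reader might infer that biologics go unrecorded. The CRF does not support that: items 9 and 10 can both hold a biologic, and the emphasis on corticosteroids in item 10 is not a restriction. What stands is that capture is generic, without a last-dose date, and that no analysis uses it.
- **The mechanism is not in the protocol.** It names no agent and no binding target. A drug that binds only a soluble mediator need not stain cells, and whether a surface target survives fixation, activation, chemical modification and serum dilution is unknown. This stands. The claim is that exposed serum can stain, not that it will.
- **The eosinophil threshold limits exposure.** Section 7.1 requires at least 0.3 × 10⁹/L for severe eosinophilic asthma, which may keep out some effectively treated patients. This stands in part: the timing of the count is not stated, and EGPA has no threshold.
- **Staining is not the endpoint.** It is tempting to call this a false positive built into the primary objective. The text does not go that far. The ROC analyses concern blood auto-antibodies, which section 6 places after candidate auto-antigens have been identified, and nothing says raw fluorescence intensity enters them. ELISA targets come from literature review and gene-set analysis. Confocal and marker work also lies between staining and a named antigen, though it is not planned as an interference check.
- **It is a pilot with replication intended.** True, but replication in similarly treated patients would not remove the artefact.

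**Conclusion.** The concern holds in conditional form and should be addressed. As written, the plan cannot separate a cell-binding therapeutic antibody from an auto-antibody in the immunofluorescence arm, and exposure would sit essentially in cases alone. This is a gap in design and analysis, not merely a missing detail.

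The size depends on exposure that the protocol does not give. At 10-25% of 60 cases the worst case is 6-15 spurious positives, with an AUC of 0.55-0.63 only if that reading were used in a ROC analysis. These are upper bounds for the stated exposure, because they assume that every exposed serum reads above every control. At zero exposure the bias is zero.

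A reader might also infer that exposed patients ought to be excluded. The documents do not support that as the main rule: at the upper figure it would remove 15 of 60 core cases from this arm, by treatment status and so probably not at random.

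**What to change.** 1. In section 13.2, add one patient CRF item for therapeutic monoclonal antibodies: agent, start date and last-dose date.
2. In sections 10.2 and 14, pre-state that immunofluorescence positivity is reported separately for exposed and unexposed patients, with a sensitivity analysis that leaves out exposed samples, and that both are examined before any staining is called a novel auto-antibody.

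The informative comparison is unexposed patients against controls. The exposed-versus-unexposed contrast is descriptive, because treatment is likely to follow disease severity.

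**Cost.** One CRF item and a less precise sensitivity analysis in one arm. Leaving out 6 of 60 cases widens the standard error of case positivity by √(60/54) = 1.05, or about 5%; leaving out 15 widens it by √(60/45) = 1.15, or about 15%. The full-sample result is still reported. Eligibility, patients' treatment and the ELISA arm do not change.
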